## **Measures**

**SCID DSM-5.** If a participant reports frequent drug or alcohol use, they will fill out questionnaires on their DSM-5 symptoms for the respective substance (other than tobacco). Data will be recorded on Qualtrics, only identified by participant ID.

*Wide Range Achievement Test 4 (WRAT 4).* A reading survey to measure participant's grade-level equivalent reading ability. This will be administered at the baseline session. Data will be recorded on paper, only identified by participant ID.

*Single Commodity Delay Discounting (DD).* A binary choice procedure will be conducted on a personal computer to assess DD. On each DD trial, two hypothetical money rewards will be presented on the screen. One outcome will be an amount of money available immediately; the other outcome will be a larger amount of money (\$50, \$1,000) available after some specified delay (1 week, 1 month, 6 months, 1 year, 5 years). Participants will indicate the preferred alternative with a mouse-click, and the computerized algorithm (Holt et al., 2003) will adjust the immediate reward over 6 trials to determine an indifference point for each amount/delay pairing, resulting in 7 indifference points (corresponding to the 7 delays) for each of 2 amounts (\$50\$1,000). Indifference points will be used to calculate delay discounting rates. Participants will be told to indicate preference on the task as if the outcomes were for real money; previous research has established the validity and reliability of DD tasks for hypothetical rewards (Matusiewicz et al., 2013). The results of this assessment will be recorded on a laptop computer, only identified by participant ID.

*Timeline Follow-Back (TLFB; Sobell & Sobell, 1992).* A 7-day TLFB methodology will be employed to assess point prevalence of tobacco use. Participants will be asked to report number of cigarettes smoked for each day. Participants will also be asked to report nicotine vape and marijuana use. Data will be recorded on Qualtrics, only identified by participant ID.

*Tower of Hanoi (ToH).* This assessment consists of a board with 3 pegs and 4 disks of differing sizes. Participants must move the stack of disks from one peg to another while following specific rules (i.e., all pegs must end up on the farthest peg and at no point can a larger disk be placed on top of a smaller disk). Task will be completed with a research assistant and data will be recorded on Qualtrics, only identified by participant ID.

*Hopkins Verbal Learning Test – Revised (HVLT-R; Brandt & Benedict, 2001).* This standardized assessment of verbal learning and memory requires participants to memorize a list of words presented auditorily. Participants are then asked to recall or recognize as many words as possible, either immediately or following a delay. Task will be completed with a research assistant and data will be recorded on Qualtrics, only identified by participant ID.

*Letter Number Sequencing (LNS).* This measure of working memory is in the Adult Intelligence Scales–III (Wechsler, 1997). The participant is given a mixed string of letters and numbers that they must then put into a sequential order of numbers followed by a sequential order of letters. The string presentation increases in difficulty until the participant is no longer able to correctly sequence three strings of equivalent difficulty. Task will be completed with a research assistant and data will be recorded on Qualtrics, only identified by participant ID.

*Fagerstrom Test for Nicotine Dependence (FTND; Heatherton et al., 1991).* Nicotine dependence will be measured using the 6-item FTND, a standard instrument for assessing intensity of physical addiction to nicotine as it relates to smoking. Data will be recorded on Qualtrics, only identified by participant ID.

*Expired Breath Carbon Monoxide (CO).* Smoking status will be measured with an expired carbon monoxide (CO) level using a coVita Micro+basic Smokerlyzer monitor (<https://www.covita.net/product/microbasic-smokerlyzer/>). A CO level below 9 parts per million will indicate smoking abstinence for 12 hours or less. Trained research staff will administer this measure. Disposable mouthpieces will be used for each individual, and the results will be shared with the participants immediately following completion if they are interested. Data will be recorded on the CO monitor and on Qualtrics, only identified by participant ID.

*Salivary Cotinine.* Smoking status will also be measured with a salivary cotinine measure (saliva sample) using NicConfirm mouth swab cotinine tests (<https://www.confirmbiosciences.com/products/retail-brands/nicconfirm-swab-cotinine-test/>). A cotinine level below 30 ng/ml will indicate smoking abstinence for 1 week or less. The results will be shared with the participants immediately following completion if they

are interested. Data will be recorded on Qualtrics, and a picture will be taken of the salivary cotinine test for record-keeping, only identified by participant ID.

### Timeline

Measure	Screener Call	Baseline	Computer Training (CT) [-3-5 weeks]	Post-CT	1-week Post-Quit Date	1-Month Post-Quit Date
Screener	X					
Demographics		X				
DD Tasks		X		X	X	X
Saliva Sample				X	X	X
Breath Sample		X		X	X	X
Timeline Followback		X		X	X	X
WM Measures		X		X		X

Behavioral Activation Groups

**F. Risk/benefit assessment:** The risks associated with participation are minor, but there may be some risks possible: 1) Loss of confidentiality. This risk will be minimized by removing any link between personal information and data collection. 2) Embarrassment or negative feelings regarding their health behaviors or concerns. Participants can choose not to answer any questions. Information collected will be used for research purposes only. Participants will also be reminded that participation is completely voluntary and that they may withdraw at any time without penalty or losing any benefits to which they would otherwise qualify. 3) Minor physical discomfort from when giving saliva sample and carbon monoxide breath sample. We will do our best to minimize discomfort.

1. Physical risk: N/A

2. Psychological risk: N/A

3. Social risk: N/A

4. Economic risk: N/A

5. Potential benefit(s) of participating in the study:

- i. Participants are not guaranteed any benefits but may benefit from WM training and/or behavioral therapy centered on smoking cessation.
- ii. N/A.
- iii. This study may provide scientific and societal benefits by supporting this novel approach to improving health behaviors and outcomes via working memory training training.

**G. Location where study will be performed:** Research activities will take place at the Mazuma building in Kansas City ([name]) in office space currently rented out by KUMC staff (including [name]). The behavioral activation groups will occur remotely on Zoom.

**H. Collaboration (with another institution, if applicable):** N/A.

**I. Single IRB Review for a Multi-site study (if applicable):** N/A.

**J. Community-Based Participatory Research (if applicable):** N/A.

## **L. Assessment of Subject Safety and Development of a Data and Safety Monitoring Plan**

1. Details of the plan include:
  - a. Persons/groups who will review the data (study team; independent safety monitor, data monitoring committee or formal DSMB). [name], [name], and [name].
  - b. Data/events that will be reviewed. Dates and events will be reviewed by the PI's and the research coordinator.
  - c. Frequency of review will occur biweekly.
  - d. Safety-related triggers that would cause the PI to stop or alter the study include COVID-19 infection or increased risk and cases in the greater Kansas City area.
2. Events will be determined as serious if they adversely impact the mental or physical health of the participant. Any AE will be reported to the PI immediately, and the PI will make the determination if the event is an AE or SAE and related or unrelated to the study. Any SAE that is related to the study will be reported within 24 hours of the determination to the IRB as well as funding agency. AE/SAEs that are unrelated to the study will be reported during regular reporting intervals.
3. If a participant has an adverse experience during the study, study participation will be discontinued for the participant.

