**D. Subject Criteria (See Vulnerable Populations appendix, if applicable):** The subject age range will be over 18 years old. Participants will be able to participate in the study regardless of gender and race. Special populations, such as minors and pregnant women, will not be targeted for inclusion.

1. **Inclusion criteria:** To be included in this study, a participant must be 18 years of age or older, who have smoked at least four cigarettes per day for at least 6 months, are interested in quitting cigarette smoking, are at or below the federal poverty line based on persons in family/household and annual household income:

- 1 -- \$12,880
- 2 -- \$17,420
- 3 -- \$21,960
- 4 -- \$26,500
- 5 -- \$31,040
- 6 -- \$35,580
- 7 -- \$40,120
- 8 -- \$44,660
- $\geq 9$  – add \$4,540 for each additional person,

OR they or their child(ren) utilize a federal program for low-income individuals, and are willing to participate in a 5-week working memory training program as a pretreatment adjunct to behavioral group therapy.

2. **Exclusion criteria:** Participants must not indicate a severe substance use disorder according to the DSM-V with any substance other than tobacco or have any significant medical or psychiatric condition. Such conditions could include traumatic brain injury, dementia, significant learning disability, or psychotic symptoms. Participants must be at least at a 5th- grade reading level. In case that participants are excluded, they will be provided with

resources in the community and provided with contact information for the Kansas Tobacco Quitline.

3. **Withdrawal/Termination criteria:** Participants may withdraw from the study at any time without penalty. The researcher reserves the right to discontinue individuals who evidence inability to comply to study conditions. The researcher will also exclude participants if they seem at risk for COVID-19 infection.
4. Participants can partake in other studies while participating in this research study if it does not interfere with their method of smoking cigarettes.

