**Baseline session:** This session will take approximately 1 to 1.5 hour to complete and will include informed consent and initial assessments. Participants will complete an informed consent process, which will include time and space to read the informed consent form (ICF), followed by thorough discussion with a study staff member about the nature of the study, potential risks and benefits, and participant rights. If the individual wishes to continue following this discussion, they will digitally sign the ICF via Qualtrics. At the point at which the ICF is signed by the individual, s/he will be considered an enrolled participant. Participants will also report demographic information (age, sex, race/ethnicity, current income, employment, and education level) and report on their cigarette smoking behavior. If at any point during the study a participant reports elevated suicidality, they will be thoroughly assessed for suicidality risk by the PI, who has extensive clinical experience, and participants will be referred to immediate care (e.g., Emergency department, Kansas City crisis response) depending on level of risk. All individuals will be provided with a referral document which lists medical, substance use, and case management services in the Kansas City area. Participants will also complete a reading test (Wide Range Achievement Test-4; WRAT-4) to confirm reading level from self-reported educational attainment.

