4. Session 4 (quit week): Clinician will go over participants' use of the Daily Activity, Mood, and Smoking log, discuss quit dates and quitting experience (e.g., withdrawal and immediate plans) for each participant, discuss success in accomplishing LAVA activities, identify obstacles to abstinence, offer support, talk about maintaining a healthy lifestyle (i.e., proper diet and exercise), and highlight social support, particularly by encouraging participants to form a "Contract" with a supportive person in their life (i.e., ask someone to take part in an activity with them to help them remain abstinent, such as riding bicycles together).
5. Session 5: Clinician will go over participants' use of the Daily Activity, Mood, and Smoking log, participants' contracts, quitting experience (e.g., withdrawal symptoms), strategies to avoid smoking, perceived benefits and disadvantages to quitting smoking, and identifying high-risk situations.
6. Session 6: Clinician will go over participants' use of the Daily Activity, Mood, and Smoking log, quitting experience (e.g., withdrawal symptoms), strategies to avoid smoking, perceived benefits and disadvantages to quitting smoking, discuss time management as a tool for abstinence, help identify high-risk situations, and offer support.
7. Session 7: This session will mirror Session 6.
8. Session 8: This session will mirror Sessions 6 & 7, and will include a discussion on developing a post-program plan to maintain abstinence by engaging and monitoring activities after the BA group and dealing with negative feelings, triggers, and immediate cravings. The clinician will also review the overall program progress and remind participants about the upcoming follow-up sessions.

**Post-training session:** This session is expected to take 1 to 1.5 hours to complete. 2-3 days following their last training session, participants will complete the DD task, TLFB, TOH, HVLT-R, LNS, and provide a CO breath sample. Participants will be asked to set a quit date for their cigarette smoking at this session and will be encouraged to connect to the tobacco quitline ([name]).

**1-week post quit date session:** This session is expected to take about 30 minutes to complete. Around 7 days after their quit date, participants will complete the DD task, TLFB, and provide a CO breath sample. Participants will also provide a saliva sample to test for salivary cotinine, a metabolite of nicotine to biochemically verify smoking status/abstinence.

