**1-month post quit date session:** This session is expected to take about 45 minutes to complete. Around 30 days after their quit date, participants will complete the DD task, TLFB, TOH, HVLT-R, LNS, provide a CO breath sample, and provide a saliva sample.

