## **V. Data Analysis and Reporting**

**A. Statistical and Data Analysis:** Hypotheses encompassed within Aim 1 will be tested using Hierarchical Linear Modeling (HLM; Raudenbusch & Bryk, 2002), which allows the analysis of repeated measures and has been recommended because of its ability to: 1) accommodate missing data, 2) examine individual change over time in outcomes, and 3) include the average change and the individual variation around this average change which is especially important in a small sample (Raudenbusch & Bryk, 2002; Singer. & Willett, 2003), even in smaller samples (Collado et al., 2019).

- B. Outcome:** The study will conclude once we collect full data from 10 participants. It is expected that study hypotheses will be supported, with success/failure determined by results from WM training on cigarette use over time.
- C. Study results to participants:** Participants will be given information on their breath/saliva samples results immediately following testing if they are interested.
- D. Publication Plan:** Data will be used to support a subsequent NIH grant application. Attempts to publish in relevant peer-reviewed journal will made if hypotheses are sufficiently supported.

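### Section II.L item 3 ends study participation after any adverse experience, so outcome assessments stop with the intervention; separate the two and keep assessing those who agree

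*Combined protocol and SAP*

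**What the plan says.** Section II.L item 3 reads: "If a participant has an adverse experience during the study, study participation will be discontinued for the participant". Item 2, just above it, has the PI classify each event as AE or SAE and as related or unrelated, but item 3 uses neither distinction. Item 2's threshold for seriousness is itself low: "Events will be determined as serious if they adversely impact the mental or physical health of the participant".

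The withdrawal and termination criteria in II.D item 3 allow voluntary withdrawal, add that "The researcher reserves the right to discontinue individuals who evidence inability to comply to study conditions", and exclude people who seem at risk of COVID-19. They do not mention adverse experiences, and they describe no follow-up after discontinuation.

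Two other places deal with particular health events. The baseline-session text says "If at any point during the study a participant reports elevated suicidality, they will be thoroughly assessed for suicidality risk by the PI", with referral to care according to risk. The COVID-19 procedures ask someone with symptoms to leave and contact the health service. Neither says that participation ends for that reason.

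After training, outcomes are collected at three visits: post-training, 1 week after the quit date ("Around 7 days after their quit date, participants will complete the DD task, TLFB, and provide a CO breath sample") and 1 month after it ("Around 30 days after their quit date, participants will complete the DD task, TLFB, TOH, HVLT-R, LNS", plus breath and saliva samples). Section V.A states that "Hypotheses encompassed within Aim 1 will be tested using Hierarchical Linear Modeling". Section V.B judges success on cigarette use over time.

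**The concern.** Assessment visits are part of study participation, so on its plain wording item 3 ends them together with training and groups. Someone stopped during training leaves only a baseline record and contributes no within-person change. Someone stopped at any time before the 1-week visit leaves no post-quit smoking record, and that is the outcome on which success is judged.

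The loss need not be unrelated to outcome. The group sessions themselves discuss withdrawal symptoms and negative feelings around quitting, and a person who has an adverse experience may smoke differently afterwards from one who does not. The hierarchical model can use records made before the stop. It gives valid answers only if, given those records, the loss does not depend on the smoking that was never observed. The plan states no such assumption and offers no sensitivity analysis.

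**Working it through.** The plan has no figure to reproduce here: it gives no adverse-event rate, dropout rate or power calculation. The check has four parts.

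**1. Does anything continue assessments after a stop?** The places where such a provision would sit are II.D item 3 (termination), the COVID-19 procedures, the visit descriptions, the timeline table, II.L and V.A. None contains one. The material between II.J and II.L was not available for this check.

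**2. What does one stop lose?** From the visit descriptions and the timeline table:
- Timeline Followback, breath CO and delay discounting: baseline, post-training, 1 week, 1 month = 4 rounds.
- Working-memory measures: baseline, post-training, 1 month = 3 rounds.
- Post-quit visits: 1 week, 1 month = 2.

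Rounds lost = rounds planned − rounds done before the stop. Payments for the missed visits are $35, $30 and $30 (payment section).

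| Time of stop | TLFB/CO/DD lost | WM lost | Post-quit visits lost | Payment for missed visits |
|---|---|---|---|---|
| During training | 4 − 1 = 3 of 4 | 3 − 1 = 2 of 3 | 2 of 2 | 35 + 30 + 30 = $95 |
| After post-training, before 1 week | 4 − 2 = 2 of 4 | 3 − 2 = 1 of 3 | 2 of 2 | 30 + 30 = $60 |
| After 1 week, before 1 month | 4 − 3 = 1 of 4 | 3 − 2 = 1 of 3 | 1 of 2 | $30 |

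These counts need no assumption about rates.

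**3. What happens to the sample?** Section II.C speaks of 15 completers, and V.B ends the study once full data exist on 10 people. Both count finished participants, not enrolled ones, so a stopped person is replaced. If a share p of those enrolled is stopped (an assumption), reaching N non-stopped participants takes N/(1 − p) enrolled, of whom N·p/(1 − p) are stopped.

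| Assumed p | N = 10: enrolled (rounded up) / stopped | N = 15: enrolled (rounded up) / stopped |
|---|---|---|
| 10% | 11.1 (12) / 1.11 | 16.7 (17) / 1.67 |
| 20% | 12.5 (13) / 2.50 | 18.75 (19) / 3.75 |
| 30% | 14.3 (15) / 4.29 | 21.4 (22) / 6.43 |

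**4. Is there a bias figure?** For a simple abstinence proportion, using only those not stopped would shift the result by p × (abstinence in those not stopped − abstinence in those stopped). The documents give none of these three quantities, so neither size nor sign follows.

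**The case against.** The best reply is that item 3 is loose drafting, not a settled plan to remove everyone with any event. Item 2 sets out reporting and classification, and COVID-like symptoms and suicidality are each handled without stating discontinuation. The risk section calls the risks minor and lists physical and psychological risk as not applicable, and nothing shows that staff would log brief discomfort as an adverse experience. This is also an exploratory, open-label Stage 1a pilot with no stated power to protect, and a cautious stopping rule is partly a safety choice for the PI and the IRB.

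Much of that stands, and it lowers the weight of the point. It does not remove it. The other provisions cover reporting or particular events, so item 3 remains the only general statement on participation after an adverse experience, and staff have to follow what is written. If something narrower was meant, the same short edit is needed.

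A reader might infer three stronger things that the documents do not support:
- That a given share of 20 or 30 planned post-quit visits will be lost. Since 10 and 15 are targets for finished participants, stopped people are replaced and the final set keeps its visits. The loss shows up as extra enrolment and selection.
- That the smoking result will look too favourable. That direction would need outcome data on stopped people.
- That item 3 is the only provision on health events. It is not, as shown above.

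**Conclusion.** The point holds, with modest weight. As written, item 3 ends outcome assessment as well as intervention after an adverse experience of any severity or cause. Per person, the loss ranges from one assessment visit to all three that follow baseline. For the trial, the consequence is extra enrolment and a finished sample selected on having had no adverse experience, which the hierarchical model does not repair by itself if loss depends on unobserved smoking.

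This rests on reading study participation as including the assessment visits, which is the natural reading, and on no provision elsewhere continuing them. The enrolment figures depend on assumed stop rates of 10 to 30%.

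**What to change.** Replace II.L item 3 with wording such as:

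> Training and group sessions will be stopped for a participant with a study-related serious adverse event, and may be stopped for other adverse events at the PI's clinical judgement. Unless consent is withdrawn or the PI judges assessment unsafe, the participant will be invited to complete the remaining assessments, and all data will be included in the HLM. The date and reason for the stop will be recorded.

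Four additions make it workable:
- Cross-refer to it in the termination criteria (II.D item 3).
- Give a timing rule. A quit date may be set in group Session 3 or at the post-training visit ("Participants will be asked to set a quit date for their cigarette smoking at this session"); use it if it exists. Otherwise time the remaining visits from the stop date, code them in the model by actual time since baseline, and do not label them post-quit.
- State that stopped participants who complete the remaining assessments count toward the data targets.
- Ask the PI and IRB whether item 2's definition of serious needs a severity threshold, because the mandatory stop now depends on it.

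**Cost.** At most $95 per stopped person, in payments and visits already in the plan (transport is included in the payments), plus staff time. Total = 95 × N·p/(1 − p), if every stop occurs during training and everyone agrees to be assessed:
- N = 10: 95 × 1.11 ≈ $106, 95 × 2.50 ≈ $238 and 95 × 4.29 ≈ $407 at assumed stop rates of 10, 20 and 30%.
- N = 15: about $158, $356 and $611.

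These totals assume enrolment continues until N people finish without a stop; counting stopped people who complete their assessments would reduce the need for replacements.

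**If follow-up is already over.** Section II.C is written in the past tense and V.B in the future, so trial status is unclear. In that case, report the number stopped under item 3 with dates and reasons, and keep their earlier records in the model.
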